- 1) Whole brain, ventricular and caudate volumes, and rates of atrophy using the boundary shift integral (BSSI) (BBSI) (Freeborough & Fox, 1997)
- 2) Assessment of diffusion metrics and fibre tracking from Diffusion Weighted Imaging (DWI)
- 3) Assessment of neurite density using Neurite Orientation and Dispersion Diffusion Imaging (NODDI) to detect subtle changes in microstructure which are complementary to macrostructural information provided by volumetric imaging (London and Paris only)
- 4) Grey- and white-matter density using voxel-based morphometry (VBM) (Ashburner & Friston, 2000)
- 5) Automated segmentation of regions of interest including caudate and putamen using the Brain Research: Analysis of Images, Networks, and Systems (BRAINS, Magnotta et al. 2002) software which integrates reliable and validated image analysis tools for large neuroimaging studies.
- 6) Resting state fMRI region analyses and principal component analyses.
- 7) FMRI activation data, correlating the onset of a movement with the changes in blood oxygenation caused by it, and analyses of functional and effective connectivity. The analysis of fMRI data is well established and uses SPM. Two well established fMRI activation studies will be performed. One task involves finger movements following visual and auditory stimuli. Movements differ in speed and complexity, and some may require the participant to withhold a movement. The second task focuses on memory and participants need to memorise numbers or objects and recall them later.
- 8) Magnetic resonance spectroscopy to detect changes in metabolites indicative of neuronal health (Vancouver and Leiden only)
- 9) CEST chemical exchange rate analysis to indirectly image protein accumulation in its soluble form, and in particular HTT, thought to be the earliest characteristic of HD (Vancouver and Leiden only)
- 10) MTR to detect levels of aggregated mutant HTT and disease-related microstructural change. (Vancouver and Leiden only).

In addition, Track-HD and CHDI support the widest possible use of these data for scientific purposes. The full imaging datasets will therefore be made available for legitimate research purposes on request subject to agreement of the steering committee. For full details on Data sharing, see section 5.19.2.

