5.7. The TRACK-HD Day

Each participant will see a site neurologist and psychologist (P). Ideally, each assessment should take place at the same time of day in each centre. In practice this may not be possible owing to staff and scanner availability. Timings will be recorded as meta-data to allow analysis of the effect of time of day on outcomes. Timings allow for time to move between departments, and short comfort breaks. Participants are offered more refreshments at the beginning of the assessments as well, as required. A timetable for a participant visit is shown in Table 11.

Time	Assessment Type	Details	Duration
In adv	ance of visit	Neurologist prepares consent form, information sheet, MR Psychologist collates necessary testing forms, sets up relev Neurologist ensures adequate sample tubes, equipment, que	ant computer programs
09.30	General	UHDRS, medical history, co-morbidity, demographics, biosamples, buccal swab	30 min
		Positioning	2-10 min*
		1 x T1 scans (if imaging quality poor a repeat T1 may replace MRS)	12 min
		Resting fMRI	15 min
		Field map	2 min
		Amide CEST and MTR (Vancouver and Leiden)	15 min
		DWI (London and Paris)	10 min
		MRS (Leiden and Vancouver)	
10.30	Imaging	Break	10 min
		Training for activation fMRI tasks (outside scanner)	5-10 min
		Positioning	2 -10 min*
		Task-related fMRI: (Working memory – London and Paris; Motor task – Vancouver and Leiden)	15 min
		Field map	2 min
		NODDI (London and Paris)	25 min
		DWI (Vancovuer and Leiden only)	5 min
		1 x T2 scan	12 min
12:30		LUNCH	
13:30	Cognitive	SDMT Stroop IQ covariate Visual array task Map search Mental rotation Paced tapping (3Hz) Circle tracing with backward counting Cancellation task Virtual maze task	50 min
14:30	Quantitative Motor	Manumotography Force matching Digitomotography Dysdiadochomotography Choreomotography Pedomotography Posturography Posturography Go-No-Go task	45 min

15:30	Neuropsychiatric & Functional	HADS BDI FrSBE# BAIS#	20 min
16:15	TMS	Transcranial Magnetic Stimulation/Electromyography Hot spot determination, Cortical silent periods Somatosensory evoked potentials, Long-latency reflexes, Visual evoked potentials, TMS evoked potential,	45 min

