5.15.2. Secondary questions for TRACK-HD

- 1. What is the earliest point during the premanifest disease process at which longitudinal effect sizes for any measure become sufficient to useful in a clinical trial?
- 2. What are the key demographic and clinical variables that must be taken into account to maximize measure sensitivity, such as age, education level, IQ, sex, etc.?

Analytical comments:

- a) It will be impossible to know the true time from diagnosis for premanifest participants who do not show substantial signs of developing illness during the course of the study. Therefore, estimates of earliest detectable longitudinal changes will rely partly on comparisons to separate, already validated prognostic indicators. For example, we will test relationships between longitudinal change and CAG-age based estimated time until diagnosis and striatal volumes.
- b) As discussed in 5.14, potential demographic and clinical confounders, as identified by the investigators, will be controlled as statistical covariates in the longitudinal and other analytical models.

Revised: 2nd September 2013 73 Version 5.2

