5.15.9. Imaging data analysis

T1- and T2- weighted images

Measures will include: VBM (Ashburner & Friston, 2000); BSI-derived rates for whole brain and caudate, atrophy and ventricular expansion (Freeborough & Fox, 1997); volumes from automated segmentation of striatal structures (Magnotta et al. 2002);. Cross-comparisons between each of these image-analysis methods will be undertaken.

Diffusion weighted imaging and Neurite Orientation and Dispersion Diffusion Imaging (NODDI)

We plan to perform well established compound measures of white matter integrity (e.g. fractional anisotropy, mean diffusivity, axial and radial diffusion, etc.). In addition, we plan to employ probabilistic fibre tracking to

Revised: 2nd September 2013 75 Version 5.2

determine white matter connection in the brain. We will also investigate neurite orientation and dispersion using the novel NODDI image acquisition.

Resting state fMRI analyses

We plan to perform seed region analyses and well as principal component analyses.

Activation fMRI analyses

fMRI activation data will be processed by correlating the onset of a movement with the changes in blood oxygenation caused by it. In addition, we plan to perform analyses of functional and effective connectivity. The analysis of fMRI data is well established and uses SPM .

Amide CEST and MTR

Levels of soluble and aggregated mutant HTT will be assessed using CEST and MTR image acquisitions respectively.

Each imaging measure will be assessed individually by determining the sample sizes needed in order to detect (with sufficient power) disease-modifying effects of various magnitudes. This will allow imaging measures to be compared, both with each other and with the other clinical phenotypic parameters. Secondary analyses will look at the associations between imaging measures and other measures (clinical assessments, CAG length, CAG-age prognosis, cognitive profile, neuropsychiatric scores, motor assessment, functional measures, wet biomarker profiling etc.). Note that, in addition to the usual CAG-age prognosis, CAG length is of separate interest for imaging and other biological markers, as modification of the huntingtin protein's biological effect is a function of CAG length.

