5.16. Sample size considerations

While sample size estimates can be calculated from the literature for individual measures for desired power, significance and effect sizes, this exercise can only be performed reliably over the interval originally studied. Extrapolated sample size estimates for other observation intervals or longer follow-up periods may be notably more inaccurate. Moreover, one of our aims is to generate multivariate, multimodal data with high temporal resolution. Until the desired measures have been made simultaneously, calculations cannot be performed to determine the required sample size for reliably identifying the optimum multimodal battery of measures in premanifest and early HD, or calculating the cohort size required for such a battery to be able to detect the effect of a disease modifying intervention.

Sample size estimates for TRACK-HD visits 5, 6 and 7 are based on the number of eligible PM and control participants available at the time of the calculation, which is approximately 123 PM and 102 controls. For potential longitudinal follow-up we assume a 10% loss in each of the groups, yielding 110 CAG-expanded and 92 controls. However, additional participants will be recruited in each group as specified above.

As of visit 4, few convincing longitudinal differences between PM participants and controls have been detectable. For measures continued since the study's inception, the additional 12 to 36 months of follow-up gained by visits 5, 6 and 7 will provide substantially greater power to detect meaningful longitudinal separation of the disease path. The precise increase in power depends on extrapolation of several assumptions about how within-participant measures continue to correlate over time. The nature of this continuing correlation may vary, depending on the measure, and is difficult to predict on the basis of the currently available observations. However, within a realistic range of continuing assumptions, visit 5 follow-up should allow us equivalent power to detect changes that are between 75% and 89% the effect detectable after visit 4 of the study of the study. At

visit 6, when total follow-up is 60 months, we will be able to detect effects between 58% and 80% of those detectable at 36 months of follow-up.

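### For change in segmented striatal volume, striatal volume is not a separate prognostic indicator: shared scan error biases the planned test, in a direction set by which visit's volume is used

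*Protocol*

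**What the plan says.** Section 5.15.2 asks how early in the premanifest course the longitudinal effect size of any measure becomes large enough for a trial. True time to diagnosis is unknown for most participants, so comment (a) says "estimates of earliest detectable longitudinal changes will rely partly on comparisons to separate, already validated prognostic indicators". As an example it continues: "we will test relationships between longitudinal change and CAG-age based estimated time until diagnosis and striatal volumes". It does not say which visit's striatal volume is meant and does not set striatal outcomes apart.

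Striatal measures are also outcomes. Section 5.5.9 lists "Automated segmentation of regions of interest including caudate and putamen", and 5.15.9 lists "BSI-derived rates for whole brain and caudate, atrophy and ventricular expansion (Freeborough & Fox, 1997); volumes from automated segmentation of striatal structures". The timetable in 5.7 (Table 11) has "1 x T1 scans (if imaging quality poor a repeat T1 may replace MRS", so a visit normally yields one usable T1 image.

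Section 5.14.1 recognises imperfect reliability and regression towards the mean, as part of what change in the control group reflects. Section 5.14.2 plans mixed models with linear time and bases prognosis within the premanifest group on CAG and age.

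**The concern.** An indicator used to stage participants should carry no error in common with the outcome it is tested against. CAG-age meets that condition. Striatal volume meets it for cognitive, motor or other non-imaging outcomes. It does not meet it when the outcome is change in striatal volume computed from the same images: a baseline volume measured too high makes the later loss look too large. The expected correlation is then not zero when stage and rate of change are unrelated, so the usual test no longer tests that hypothesis.

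In the disease, smaller striata would be expected to lose volume faster, which is a positive correlation between volume and signed change. Error shared with the first scan pushes the other way. At stake is whether, for segmented striatal volumes, the gradient of change against stage can be read at all. Section 5.2 reports structural change in premanifest participants with no reliable functional marker at 24 months, so imaging outcomes are where the earliest-change question matters most.

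**Working it through.** **Inputs from the protocol.** Section 5.16 gives "approximately 123 PM and 102 controls", and "we assume a 10% loss in each of the groups". 123 × 0.9 = 110.7 and 102 × 0.9 = 91.8, which agree within rounding with the stated 110 and 92. I use n = 110 premanifest.

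**Assumed, because the protocol gives no value.** Reliability R of segmented striatal volume; SD s of true change between people, in units of the between-person SD of measured volume; a two-sided 5% test.

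**Two scans, first-visit volume.** Let V1 = T + e1 and V2 = T + D + e2, with Var(V1) = 1, error variance 1 − R, Var(D) = s² and Corr(T, D) = ρ. Change is D + e2 − e1. Then

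r = [ρ·s·√R − (1 − R)] / √(s² + 2(1 − R)).

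With a volume whose error is independent of both scans, the term −(1 − R) in the numerator disappears.

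*No true relationship* (ρ = 0), s² = 1 − R, Fisher z with standard error 1/√107 = 0.0967:

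| R | r | abs(z)/SE | Rejects at 5% |
|---|---|---|---|
| 0.90 | −0.10/√0.30 = −0.183 | 1.91 | 48% |
| 0.95 | −0.05/√0.15 = −0.129 | 1.34 | 27% |
| 0.98 | −0.02/√0.06 = −0.082 | 0.85 | 13.5% |
| 0.99 | −0.01/√0.03 = −0.058 | 0.60 | 9% |

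*True ρ = +0.3* (smaller striatum, faster loss). At R = 0.95, ρ·s·√R = 0.3 × √(0.05 × 0.95) = 0.065. First-visit volume gives r = (0.065 − 0.05)/0.387 = 0.040 and 6% power in the right direction; an independent volume gives 0.065/0.387 = 0.169 and 42%. At R = 0.98 the powers are 15% and 43%.

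**More visits.** Simulation: 3,000 runs per cell, n = 110, a least-squares slope per person over annual visits, R = 0.95, annual s = 0.05:

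| Visits | False rejection, first-visit volume | Mean r if ρ = +0.3 | Right-direction detection, first-visit volume | Same, independent volume |
|---|---|---|---|---|
| 2 | 37% | −0.11 | 0.0% | 6.9% |
| 3 | 36% | −0.06 | 0.5% | 14.9% |
| 4 | 30% | −0.01 | 2.1% | 26.2% |
| 7 | 14% | +0.14 | 30.6% | 65.2% |

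Over the whole grid (R 0.80 to 0.99, s 0 to 0.10, 2 to 7 visits), false rejection with first-visit volume runs from 4.8% to 93%. An indicator with independent error stays between 4.1% and 5.4%. At R = 0.99 and seven visits, false rejection is 5.4% for s = 0.05, 4.8% for s = 0.10, and 9.6% if everyone has the same true change. In the s = 0.10 cell, detection at ρ = +0.3 is 85.5% against 88.0% with the independent volume.

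**Last-visit volume.** The error now enters with a plus sign. For two scans, R = 0.95 and s = 0.05, the covariance at ρ = 0 is s² + (1 − R) = 0.0025 + 0.05 = 0.0525, nearly all of it error. Over 2 to 7 visits the simulated mean r is +0.16 to +0.30 and rejection 41% to 89%; part of that, growing with follow-up, is real accumulated loss.

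**The case against.** The strongest defence is that the protocol never writes down the faulty analysis. Comment (a) covers all domains, offers striatal volume as an example, and asks for separate indicators, which could be read as excluding a measure that is itself the outcome. The secondary associations named for imaging in 5.15.9 include CAG length and CAG-age prognosis, and striatal volume is not among those named. The question is secondary and relies only partly on these comparisons. CAG-age runs alongside and is unaffected. The visit supplying the volume is ordinary analysis-plan detail.

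Much of this stands, and it limits the weight of the point. It does not remove it. Comment (a) answers a question about any measure, names striatal volume as one of the separate indicators, and makes no exception where striatal volume is also the outcome. The control comparison in 5.14.1 does not help, because subtracting control change leaves the level-change correlation within the premanifest group untouched. Leaving the visit open matters more than usual here, since that choice sets the sign of the bias.

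A reader might infer more: that the planned test will reject under no relationship and will hide a real one. The document does not support that. Masking needs first-visit volume, and no visit is named. The size depends on a reliability and a spread of true change that are not given, and it becomes small with high reliability and many visits. The boundary-shift caudate rate comes from registered scan pairs, not from subtracting two segmented volumes, so these figures do not carry over to it.

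**Conclusion.** The point holds for segmented striatal volumes (caudate, putamen) as longitudinal outcomes. There the indicator and the change can share a scan and its error, so striatal volume is not separate in the sense 5.15.2 requires. With first-visit volume the correlation is biased negatively and can mask faster loss in smaller striata; with last-visit volume it is biased positively and would exaggerate that gradient.

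Under the two-scan assumptions above, with reliability 0.90 to 0.99, a nominal 5% test against first-visit volume rejects a true null in about 48% to 9% of studies. At reliability 0.95 and annual change SD 0.05 the rate is 36% with three visits, the number 5.14.2 gives for new participants, and 14% with seven. It is near nominal at reliability 0.99 with seven visits, provided true change varies between people. All of these rates rest on assumed reliabilities and change SDs.

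Non-imaging outcomes and every comparison with CAG-age are unaffected. This is a modest but real flaw in a secondary analysis, worth correcting because the correction is so cheap.

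**What to change.** Add to 5.15.2, comment (a): for outcomes that are changes in segmented striatal volume, the stage indicator is CAG-age estimated time to diagnosis, or the relationship is estimated as the correlation between latent level and slope in a mixed model that separates residual error. As a sensitivity analysis in continuing participants only, striatal volume from a scan outside the change interval may be used. Striatal volume remains an indicator for non-imaging outcomes.

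The model-based option needs care. The unstructured within-participant covariance in 5.14.2 does not by itself separate measurement error, so random intercepts and slopes with a residual term are needed. That is four variance parameters (intercept, slope, their covariance, residual). Two visits supply only three variances and covariances; three visits supply six. At least three visits are therefore required, which the planned follow-up gives.

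The cost is wording only; no new data are needed. The downside lies in the earlier-scan option, which leaves out the 30 premanifest participants recruited at visit 5 (4.9 and 5.6.4), a quarter of the target of 4 × 30 = 120, and narrows the change interval for the rest. It should therefore stay a sensitivity analysis, with the visit 5 recruits relying on CAG-age or the model-based estimate.

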5.15.3. Functional and QoL data analysis

Data will include a variety of summary scores from ratings scales (clinician rated and self-report).

Ancillary questions and analysis plans specific to functional and QOL assessments:

- 1. What are the relationships between functional and quality of life assessments and other phenotypic and imaging measures described above?
- 2. These measurements are of special interest, as they attempt to measure a quality that has some face validity as an outcome for clinical trials. We analyzed longitudinal change in functional assessments as a function of group status and validated prognostic indicators using the methods outlined in 5.14 and 5.15.1. If measurable changes can be shown for these measures, potential associations with other Track-HD outcomes will be investigated using adjusted correlation analysis and canonical correlation methods similar to those discussed above in 5.15.1.c.

5.15.4. Neuropsychiatric data analysis

Data will include summary values from individual neuropsychiatric ratings scales (self report and clinician rated).

Ancillary questions and analysis plans specific to neuropsychiatric data

- 1. Are individual or composite neuropsychiatric measures best used as covariates or outcome measures in clinical trials?
- 2. What neuropsychiatric characteristics alter the relationships between estimated proximity to onset and variables from other domains, i.e., cognitive, quantitative motor?
- 3. Longitudinal analyses of neuropsychiatric variables as outcomes will be by principles set out in 5.14 and 5.15.1. Since (potentially fluctuating) psychiatric status may confound other measurements, especially certain aspects of cognitive and physical examination, selected neuropsychiatric measures such as depression scores and others specified by the investigators will be tested as potential confounders using methods addressed in 5.14 and 5.15.2.

5.15.5. Biomarkers in plasma data analysis

Proteomic, neuroinflammatory, transcriptomic, and metabolic markers identified from our current ongoing biomarker research initiatives will be further validated using the Track-HD plasma and RNA samples. Specific *a priori* candidates will be analyzed using the general longitudinal approach described in 5.14. Any additional screening for new candidate markers will be subject to multiple comparison corrections (e.g. false discovery rate) in assessing the probable statistical and scientific significance of the results. Changes in each of the laboratory biomarkers identified will be correlated with the clinical and imaging phenotypic data using multivariate assessments.

5.15.6. Genetic modifier data analysis studies

In collaboration with the EHDN Registry, the EHDN Genetic Modifiers working group, the HSG COHORT study and [name] (Harvard) we will use lymphoblastoid cell line DNA together with clinical and family history data for identification of genetic modifiers of age of onset and the different clinical phenotypic presentations of HD. Identification of genes that modify the pathogenic process in HD offers a direct route to validate targets for development of HD experimental therapeutics. Track-HD will provide a wide range of HD-associated phenotypes by which to identify modifier genes. Initially, the phenotypes available will be

Revised: 2nd September 2013 74 Version 5.2

derived from clinical assessments (UHDRS), but the collection of biological samples will also permit the study of additional phenotypes at the levels of RNA, protein, metabolites and cultured cells. The combination of phenotypic and genotypic information will permit analysis of relationships between individual polymorphisms and genes and the effect they have on modifying the phenotypic presentation, rate of progression and response to treatment of HD using genetic linkage and genome-wide association strategies.

5.15.7. Cognitive data analysis

Data will include summary variables from individual cognitive tasks, generally indicating either response times and number of correct items. In addition, we will use factor analyses (or other means of creating composite scores from multiple variables) and examine factor scores as dependent variables.

Ancillary questions and analysis plans specific to cognitive data

- 1. What are the key demographic and clinical variables, and the practice effects, that must be taken into account to maximize the sensitivity of the cognitive data, such as age, education level, IQ, sex, etc.?
- 2. For individual tests, how do practice effects need to be taken into account to maximize utility in the context of a clinical trial?
- 3. Longitudinal analyses will be by principles set out in 5.14 and 5.15.1. Potential confounding is addressed in 5.15.2. The use of controls to study practice effects is addressed above in 5.14.

